8.0 EVALUATIONS/MATERIAL AND DATA TO BE ACCESSIONED

Timing of protocol therapy administration, response assessment studies, and surgical interventions are based on schedules derived from the experimental design or on established standards of care. Minor unavoidable departures (up to 72 hours) from protocol directed therapy and/or disease evaluations (and up to 1 week for surgery) for valid clinical, patient and family logistical, or facility, procedure and/or anesthesia scheduling issues are acceptable (except where explicitly prohibited within the protocol)

8.1 Required Clinical, Laboratory and Disease Evaluation (See [Section 4.0](#) for eligibility criteria to start therapy)

STUDIES TO BE OBTAINED	Pre-Study	During Cycle 1	Prior to and During Cycles 2 + [^]	End of Study Treatment
History	X	X ⁶	X	X
Physical Exam	X	X ⁶	X	X
Performance Status	X			
Height, weight, BSA	X	X ⁶	X	X
Vital Signs	X	Weekly	X	X
CBC, differential, platelets ¹	X ⁷	Weekly	X ⁶	As clinically indicated
SGPT (ALT), Albumin, Bilirubin	X ⁷	X	X ⁶	As clinically indicated
Electrolytes including serum creatinine, Ca ⁺⁺ , PO ₄ , Mg ⁺⁺	X ⁷	X	X ⁶	As clinically indicated
Creatinine Clearance or GFR	X			
Pregnancy Test ²	X			
Tumor Disease Evaluation ³	X	Last week of Cycle 1	Last week of cycles 2, 4, and 6 then q 3 cycles ³	X
Tibial Radiographs (Knee X-Ray) ⁴	X		X	X
Medication Diary see Appendix VI		Weekly	X	
Pathology & Genomics Report ⁵	X			
Pharmacokinetics (Required) See Section 8.5		X		
Pharmacokinetics (Optional) See Section 8.3.5		X		
Archival Tumor Tissue for immunohistochemistry: ATM. (Required) See Section 8.6 .	X			
Tumor Tissue for Whole Genome Sequencing (Optional) Section 8.3.1	X			X
Archival Tumor Tissue for Immunohistochemistry: PGBD5 and R-Loops (Optional) Section 8.3.2	X			
Tumor Tissue for Immunohistochemistry pH2AX, pKAP1 and pATR (Optional) Section 8.3.3	X			X
Blood for ctDNA for ALT (Optional) Section 8.3.4	X			
Archival Tumor Tissue for Biobanking (Optional) Section 8.3.5	X			

[^] Studies may be obtained within 72 hours prior to the start of the subsequent cycle.

¹ If patients develop Grade 4 neutropenia or Grade 3 or 4 thrombocytopenia, CBC/differential/platelets should be checked twice per week (every 3 to 4 days) until recovery to Grade 3 neutropenia, Grade 2 thrombocytopenia, or until the criteria for dose limiting toxicity are met. For patients with hematological dose limiting toxicity, CBCs should be checked at least weekly until recovery to eligibility criteria. Please see [Section 5.2.1](#) for details.

THIS PROTOCOL IS FOR RESEARCH PURPOSES ONLY, SEE PAGE 1 FOR USAGE POLICY

- ² Women of childbearing potential require a negative pregnancy test prior to starting treatment; See [Section 4.2.1](#)
- ³ Tumor Disease Evaluation [^]should be obtained on the next consecutive cycle after initial documentation of either a PR or CR. Subsequent scans may restart 2 cycles after the confirmatory scan. Please note that for solid tumor patients, if the institutional investigator determines that the patient has progressed based on clinical or laboratory evidence, he/she may opt not to confirm this finding radiographically.
- ⁴ Tibial Radiographs should only be obtained in patients without epiphyseal closure at the time of enrollment, prior to start of therapy and if baseline tibial radiographs are open then another will be obtained after cycle 1, every 3 cycles thereafter and at the end of study treatment. The end of study treatment observation is not required, if already obtained within the final month of therapy. Reference [Section 8.7](#) for further instruction on monitoring for growth plate toxicity.
- ⁵ Tumor pathology and genomics report indicating a qualifying molecular aberration to enroll on study must be submitted via upload to MediData/RAVE. Details of genomic studies noted in [Section 4.1.3](#).
- ⁶ Must be obtained within 72 hours of the start of each cycle and on day 15 of all subsequent cycles. If patients develop Grade 4 neutropenia or Grade 3 or 4 thrombocytopenia, CBC/differential/platelets should be checked at least twice weekly (every 3-4 days) until recovery to Grade 3 neutropenia, Grade 2 thrombocytopenia or until the criteria for dose limiting toxicity are met. For patients who experience hematological dose limiting toxicity, CBCs should be checked at least weekly until recovery of ANC and platelet count to eligibility criteria. Patients who have a dose adjustment due to hematologic toxicity attributable to BAY 1895344 (elimusertib), are required to have CBCs checked once weekly to confirm the safety of this adjusted dose during the cycle. Please see [Section 6.1](#) for details.
- ⁷ If greater than 7 days from pre study labs, please collect CBC, differential, platelets, bilirubin, albumin and serum creatinine within 48 hours prior to cycle 1, dose 1. These labs must still meet eligibility to receive dose 1 (as per [Section 4.0](#)).

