5.0 TREATMENT PLAN

5.1 Overview of Treatment Plan

Week	Day	Agent
1	1-3	BAY 1895344 (elimusertib) PO BID
	4-7	
2	8-10	BAY 1895344 (elimusertib) PO BID
	11-14	
3	15-17	BAY 1895344 (elimusertib) PO BID
	18-21	
4	22-24	BAY 1895344 (elimusertib) PO BID
	25-28	End of Cycle on day 28

A cycle of therapy is considered to be 28 days. A cycle may be repeated for a total of 26 cycles, up to a total duration of therapy of approximately 24 months.

Drug doses should be adjusted based on the BSA calculated from height and weight measured within 7 days prior to the beginning of each cycle. The starting dose for patients \geq 18 years of age is 40 mg BID 3 days on and 4 days off per week.

If a patient vomits within 30 minutes after the dose of BAY 1895344 (elimusertib) is administered, that dose should NOT be repeated.

On days that BAY 1895344 (elimusertib) is due to be given, it should be administered twice daily, preferably at the same time of day each day. Take BAY 1895344 (elimusertib) on an empty stomach one (1) hour before or two (2) hours after a meal with plenty of water. If a dose of BAY 1895344 (elimusertib) is missed and it is less than 4 hours since the scheduled dosing time, the dose should be taken immediately, otherwise the dose should be skipped.

Patient or caretaker must complete the medication diary with the date, time and number of agent tablets taken each day ([see Appendix VI](#)). The medication diary should be reviewed after completion of each treatment cycle and loaded into Rave.

See [Section 5.6](#) for Therapy Delivery Maps for each cycle.

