5.2 Criteria for Starting Subsequent Cycles

A cycle may be repeated every 28 days if the patient 1) has at least stable disease 2) all pre-cycle studies required per [Section 8.1](#) meet eligibility criteria-as defined in [Section 4.0](#) and 3) is otherwise eligible to continue agent administration per the requirements in [Section 6.0](#).

5.2.1 Recommendations for Starting Each Weekly 3-day Course:

BAY 1895344 (elimusertib) is administered on a 3-day on and 4-day off schedule, repeated 4 times each cycle. Hematologic toxicities are the most common toxicities with BAY 1895344 (elimusertib). Eligibility criteria require an ANC \geq 1000/ μ L and Platelets \geq 100,000/ μ L, hence these parameters also need to be met to start any cycle (See [section 4.1.11.1](#)). Once a cycle has started, patients are required to have an ANC $>$ 500/ μ L and Platelets $>$ 50,000/ μ L within 48 hours prior to initiation of each 3 day interval of BAY 1895344 (elimusertib) administration (i.e. ANC and platelet parameters must be met (without transfusion) within 48 hours of initiation of days 8, 15, and 21). If parameters are not met, this 3-day interval of BAY 1895344 (elimusertib) will be omitted and attempted to restart the following week (e.g. day 15 or 21). If more than one 3-day block of BAY 1895344 (elimusertib) is missed within a cycle (i.e. $<$ 75% of planned therapy is given for a particular cycle), that would be considered a hematologic DLT.

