5.5 Definition of Dose-Limiting Toxicity (DLT)

DLT will be defined as any of the following events that are possibly, probably or definitely attributable to protocol therapy. The DLT observation period for the purposes of study dose-escalation (Part A) will be the first cycle of therapy. Please refer to [Section 13.5.4](#) for AE resolution definitions

Dose limiting hematological and non-hematological toxicities are defined differently.

5.5.1 Non-Hematological Dose-Limiting Toxicity:**5.5.1.1 Any Grade 3 or greater non-hematological toxicity attributable to protocol therapy with the specific exclusion of:**

- Grade 3 nausea and vomiting of < 3 days duration
- Grade 3 liver enzyme elevation, including ALT/AST/GGT that returns to Grade \leq 1 within 7 days. See [Appendix IV](#) for Adverse Event grading for liver function grading parameters in children and adolescents.

Note: For the purposes of this study the ULN for ALT is defined as 45 U/L.

- Grade 3 hypophosphatemia, hypokalemia, hypocalcemia or hypomagnesemia responsive to supplementation
- Any Grade 2 non-hematological toxicity that persists for \geq 7 days and is considered sufficiently medically significant or sufficiently intolerable by patients that it requires treatment interruption.
- Note: Allergic reactions that necessitate discontinuation of study drug will not be considered a dose-limiting toxicity.

5.5.2 Hematological dose limiting toxicity:

- Grade 4 neutropenia (ANC $< 500/\mu\text{L}$) that persists for \geq 7 days despite holding BAY 1895344 (elimusertib) for 3 days
- Grade 4 thrombocytopenia (Platelet count $< 25,000/\mu\text{L}$)
- Grade 3 thrombocytopenia (Platelet count $< 50,000/\mu\text{L}$) that persists for \geq 7 days despite holding BAY 1895344 (elimusertib) for 3 days *OR* is associated with clinically significant bleeding
- Failure to meet hematological criteria to initiate weekly dosing ([Section 5.2.1](#)) or subsequent cycles of therapy ([Section 5.2](#)) by cycle day 42 (within 14 days of planned start of the subsequent cycle) will be considered dose limiting toxicity.
- Failure to receive at least 75% of the planned number of BAY 1895344 (elimusertib) doses during any cycle (i.e., 9 of 12 planned doses) due to delays attributable to myelosuppression would be considered a hematologic DLT.

5.5.2.1 Note: Grade 3 or 4 febrile neutropenia will not be considered a dose-limiting toxicity.

5.6: THERAPY DELIVERY MAPS (TDMS) FOR CYCLE 1

Page 1 of 1

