Therapy Delivery Map – Cycle 1

This Therapy Delivery Map (TDM) relates to Cycle 1. Cycle 1 lasts 28 days. Please record the dose level in the chart below. Treatment may continue in the absence of unacceptable toxicity. Use a copy of this page once for Cycle 1.

This form is to be completed and uploaded into RAVE at the end of every cycle.

Criteria to start this cycle are listed in [Section 5.2](#). Extensive details are in [Section 5.0](#) and [Section 9.0](#).

This TDM is on 2 pages.

DRUG	ROUTE	DOSAGE	DAYS	IMPORTANT NOTES
BAY 1895344 (elimusertib) IND# [REDACTED]	Oral (Tablet)	_____ mg/m ² /dose BID Dose level 1 max dose = 40 mg BID Dose level -1 max dose = 30 mg BID Part B patients \geq 18 years old: 40 mg BID	1-3 8-10 15-17 22-24	On days that BAY 1895344 (elimusertib) is due to be given, it should be administered twice daily preferably at the same time of day each day. Take BAY 1895344 (elimusertib) one (1) hour before or two (2) hours after a meal with plenty of water.

Assigned Dose Level Ht cm Wt kg BSA m² Age \geq 18 years yes. no

Date Due	Date Given	Day	BAY 1895344 (elimusertib) Nomogram Dose mg qAM. _____ mg qPM	Studies
Enter actual dose administered below				
		PRE	_____ mg _____ mg	a-e, f*, g-i, j^, k, m#, n%, q\$, r@
		1	_____ mg _____ mg	a, b, d, e, f*, g, h, l, o&, p!
		2	_____ mg _____ mg	
		3	_____ mg _____ mg	o&
		4		
		5		
		6		
		7		
		8	_____ mg _____ mg	e, f* 1
		9	_____ mg _____ mg	
		10	_____ mg _____ mg	o&, p!
		11		
		12		
		13		
		14		
		15	_____ mg _____ mg	e, f*, 1
		16	_____ mg _____ mg	
		17	_____ mg _____ mg	
		18		
		19		
		20		
		21		
		22	_____ mg _____ mg	e, f*, j^, 1
		23	_____ mg _____ mg	
		24	_____ mg _____ mg	
		25		
		26		
		27		
		28		

* Please refer to [Section 8.1](#) for the specific timing of these observations.

Observations in Cycle 1

- a. History
- b. Physical Exam
- c. Performance Status
- d. Height, Weight, BSA
- e. Vital Signs
- f. CBC, differential, platelets: *Once weekly. If patients develop Grade 4 neutropenia or Grade 3 or 4 thrombocytopenia, CBC/differential/platelets should be checked at least twice per week (every 3-4 days) until recovery to Grade 3 neutropenia or Grade 2 thrombocytopenia, or until the criteria for dose limiting toxicity are met. For patients who experience hematological dose limiting toxicity, CBCs should be checked at least weekly until recovery of ANC and platelet count to eligibility criteria
- g. SGPT (ALT), Albumin, Bilirubin

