10.0 CRITERIA FOR REMOVAL FROM PROTOCOL THERAPY AND OFF STUDY CRITERIA

10.1 Criteria for Removal from Protocol Therapy

- a) Clinical (including physical examination or serum tumor markers) or radiographic evidence of progressive disease (See [Section 12](#))
- b) Adverse Events requiring removal from protocol therapy (See [Section 13](#)).
- c) Refusal of protocol therapy by patient/parent/guardian
- d) Non-compliance that in the opinion of the investigator does not allow for ongoing participation.
- e) Completion of 26 cycles of therapy.
- f) Physician determines removal from protocol is in the patient's best interest.
- g) Repeat eligibility studies are outside the parameters required for eligibility prior to the start of cycle 1 BAY 1895344 (elimusertib) (See [Section 4.0](#)).
- h) Study is terminated by Sponsor.
- i) Pregnancy
- j) Development of secondary malignancy

Patients who are removed from protocol therapy during Cycle 1 should continue to have the required observations in [Section 8.1](#) until the originally planned end of the cycle or until all adverse events have resolved per [Section 13.5](#) whichever happens LATER. The only exception is with documentation of the patient's withdrawal of consent. Patients who are removed from protocol therapy in subsequent cycles should have the necessary observations to ensure adequate clinical care.

Patients who are off protocol therapy are to be followed until they meet the criteria for Off Study ([see Section 10.2](#)). Ongoing adverse events, or adverse events that emerge after the patient is removed from protocol therapy, but within 30 days of the last dose of investigational agent, must be followed and reported via RAVE and CTEP-AERS (if applicable). Follow-up data will be required unless consent is withdrawn.

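### In Part A, a patient who stops after Cycle 1 can be classified as free of DLT with no required blood count after the fourth dosing block

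*Combined protocol and SAP*

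**What the plan says.** - **Window.** Section 5.5: "The DLT observation period for the purposes of study dose-escalation (Part A) will be the first cycle of therapy". The Section 5.1 table places the fourth block on Days 22-24 and has "End of Cycle on day 28".
- **Counts in Cycle 1.** Observation f of the Cycle 1 Therapy Delivery Map reads "CBC, differential, platelets: *Once weekly". The map enters it before study and on Days 1, 8, 15 and 22, with nothing on Days 23-28. Section 5.2.1 ties these counts to dosing: they are due "within 48 hours prior to initiation of each 3 day interval of BAY 1895344 (elimusertib) administration", and "If parameters are not met, this 3-day interval of BAY 1895344 (elimusertib) will be omitted".
- **Next count.** Footnote 6 to the Section 8.1 table, attached to the CBC entry for Cycles 2+: "Must be obtained within 72 hours of the start of each cycle and on day 15 of all subsequent cycles".
- **End of treatment.** The Section 8.1 table leaves the CBC to clinical indication.
- **Removal during Cycle 1.** Section 10.1 continues the Section 8.1 observations "until the originally planned end of the cycle or until all adverse events have resolved", whichever is later.
- **First scan.** Section 8.1 schedules tumor evaluation in the "Last week of Cycle 1".
- **Evaluability.** Section 11.2.1 asks a patient without DLT to have at least 75% of the prescribed dose and appropriate toxicity monitoring. It does not list which counts that means.

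**The concern.** Each of the first three blocks is followed by a required count inside the DLT window. Block 4 is followed by one only while Cycle 2 is still intended. The first scan falls in that same week, progression ends protocol therapy (Section 10.1), and Cycle 2 needs at least stable disease (Section 5.2). The patients most likely to lack the count are therefore early progressors.

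The adult DLTs in Section 2.3.2 were mainly myelosuppression. In Section 5.5.2, Grade 4 thrombocytopenia is a DLT with no duration condition, so a single count can establish it or, if never drawn, miss it. Under Section 11.3, two DLTs in up to six patients mean the MTD is exceeded. One unseen event can therefore change the dose that Section 5.3.2 carries into Part B for patients under 18.

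**Working it through.** **1. Dosing days against required counts** (Section 5.1, Cycle 1 map, Section 8.1)

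| Block | Dosing days | First required CBC after the block |
|---|---|---|
| 1 | 1-3 | Day 8 |
| 2 | 8-10 | Day 15 |
| 3 | 15-17 | Day 22 |
| 4 | 22-24 | Pre-Cycle 2 draw, if Cycle 2 is still intended |

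The counts are 7 days apart, so the next weekly point is 22 + 7 = Day 29, outside a 28-day cycle. With the 48-hour allowance the last count may be on Day 22 - 2 = Day 20, which leaves up to 28 - 20 = 8 days uncounted. Section 5.2.1 gives Day 21 where the map has Day 22. The two must be reconciled, but both precede block 4. Section 8.1 alone says only weekly, which would permit a later day in week 4, but the map and Section 5.2.1 still require nothing after Day 22.

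**2. Other provisions that might supply a count**

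- *Twice-weekly rule (Section 8.1, footnotes 1 and 6).* It needs an observed Grade 4 neutropenia or Grade 3-4 thrombocytopenia. A patient cleared for block 4 had ANC above 500 and platelets above 50,000, so that count did not trigger it. A later fall cannot trigger it without another count.
- *Section 8.2 follow-up.* It covers only phase 2 patients with long-term responses, and its CBC is again left to clinical indication.
- *Section 10.1.* It helps only a patient removed during Cycle 1 who has an unresolved adverse event. Without one, the obligation ends with the cycle.
- *Section 11.2.1.* It names no count, so a patient with every scheduled CBC can be read as adequately monitored.

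**3. Illustration of size**

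The plan states no figure to reproduce. Inputs:

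- true DLT rate p = 0.40 (assumed);
- hematologic share h = 5/6, from the adult table in Section 2.3.2, where one of six listed DLTs is fatigue;
- share of hematologic DLTs first appearing after block 4, l = 0.25 to 0.50 (assumed);
- share of patients stopping after Cycle 1, s = 0.30 or 0.50 (assumed), independent of DLT;
- every late hematologic DLT in a stopper is missed (assumed, worst case).

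Missed share m = h × l × s. Observed rate q = p(1 - m). P(0 or 1 DLT in 6) = (1 - q)^6 + 6q(1 - q)^5.

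Full ascertainment: 0.6^6 + 6 × 0.4 × 0.6^5 = 0.047 + 0.187 = 0.233.

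| s | l | m | q | P(0-1 in 6) |
|---|---|---|---|---|
| 0.30 | 0.25 | 0.0625 | 0.375 | 0.274 |
| 0.30 | 0.50 | 0.125 | 0.350 | 0.319 |
| 0.50 | 0.25 | 0.104 | 0.358 | 0.304 |
| 0.50 | 0.50 | 0.208 | 0.317 | 0.385 |

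The direction does not depend on p. At m = 0.125 the probability moves from 0.534 to 0.609 for a true rate of 0.25, and from 0.358 to 0.445 for 0.33. The calculation is for a full cohort of six; the rolling-six table can also decide on three to five patients.

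**The case against.** A reader might infer that every Part A patient who stops after Cycle 1 is scored DLT-free without a late count. The documents do not support that, for four reasons.

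- **Section 10.1 reaches further than the end of the cycle.** A patient removed during Cycle 1 with any open adverse event stays on the Section 8.1 observations, including weekly CBCs, until it resolves. Section 9.1.9 lists anemia and low neutrophils, platelets and white cells as likely (above 20%), so this may cover many stoppers.
- **Pre-Cycle 2 counts come before the decision.** Section 5.2 makes them a condition for starting the cycle, and Section 5.5.2 foresees patients who fail them. The gap needs the decision to stop to precede that draw.
- **Some stoppers never take block 4.** The scan may be done at any time in the last week.
- **Classification is not automatic.** A site may draw a clinically indicated count, Section 11.2.1 requires appropriate monitoring, and Section 14.5.2 has the study chair's evaluations reviewed weekly.

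These points narrow the affected group and stand as limits on the finding. They do not close the gap. For a patient who takes block 4, has no open adverse event and is known to be stopping before pre-Cycle 2 labs, no section requires a later count. What remains is discretion.

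A larger effect is also tempting: applying the late share to all DLTs gives 28-34% and 32-42% in place of 27-32% and 30-38%. That contradicts the assumption itself, which concerns hematologic DLTs only.

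**Conclusion.** The gap holds in limited form. A site that follows the plan exactly can leave block 4 without any blood count in a patient who then enters the decision table as without DLT. The resulting bias in the hematologic DLT rate is downward and concentrated in early progressors.

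Its size cannot be read from the documents, which give neither the share stopping after Cycle 1 nor the share of hematologic DLTs that first appear after block 4. The rise in P(0-1 DLT in 6) from 23% to 27-32% (30% stopping) or 30-38% (50% stopping) is an upper-end illustration, because it treats every late hematologic DLT in a stopper as missed. The finding itself rests on the schedule comparison and not on these figures. It should be corrected, because it concerns the endpoint that sets the pediatric dose and the remedy is small.

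**What to change.** - **Section 8.1 table (Cycle 1 and End of Study Treatment cells) and Cycle 1 map.** Require one CBC with differential and platelets after block 4 and inside the DLT window, on Days 26-28, for every Part A patient, whether or not Cycle 2 starts. State that the pre-Cycle 2 draw satisfies this, and that a count taken just after Day 28 but before any Cycle 2 dose is attributed to Cycle 1.
- **Section 11.2.1.** Name this count among the monitoring studies needed before a patient is classified as DLT-evaluable without DLT.
- **Section 5.2.1.** Reconcile Day 21 with Day 22 on the map.

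The cost is one routine blood draw in patients leaving treatment, at a point where Section 8.1 already requires history, physical exam and vital signs. An occasional patient will stay pending longer, or be replaced if the count is missed, which draws on the 20% inevaluability allowance in Section 11.1. No dose or treatment rule changes.

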8.2 Required Observations Following Completion of Protocol Therapy

The following studies are required until the patient is off study as defined in [Section 10.2](#). These observations are not applicable to patients enrolled on Part A who are not treated at the MTD/ RP2D.

See COG Late Effects Guidelines for recommended post treatment follow-up:
<http://www.survivorshipguidelines.org/>

Note: Follow-up data are expected to be submitted per the Case Report Forms (CRFs) schedule.

STUDIES TO BE OBTAINED	Every 3 Months up to 12 Months ¹ (Months 3, 6, 9, 12)	Every 6 Months up to 24 Months ¹ (Months 18, 24)	Annually up to 60 Months ¹ (Months 36, 48, 60)
History	X	X	X
Physical Exam	X	X	X
Vital Signs	X	X	X
CBC with differential ³	X	X	X
SGPT (ALT), Albumin, Bilirubin ³	X	X	X
Electrolytes, Ca++, PO4, Mg++, Creatinine ³	X	X	X
Disease evaluation ²	X	X	X

¹ Only for phase 2 cohort patients that come off protocol therapy and have long-term responses.

² Imaging studies should be obtained only if required as per standard of care or if disease progression is suggested by symptoms, physical findings, or abnormal laboratory values.

³ As clinically indicated.

8.3**Research Studies for which Patient Participation is Optional**

Every effort should be made to include these optional studies. Sites which cannot collect samples for any reason other than lack of availability should contact the study chair. If insufficient amount for all tests, the priority from highest to lowest is as follows:

